4.33 Study Completion

After the subject has completed the 2-Year follow-up visit, the Subject Termination must be recorded and completed within the EDS. During the course of the study, it is possible that subjects will be withdrawn from the study early. Factors leading to subject withdrawal may include, but are not limited to, the following:

- **Subject Withdrawal** - A subject may voluntarily withdraw from the study at any time without affecting his or her future medical treatment or benefits. In addition, the Investigator may withdraw a subject from the study if the subject refuses further testing or follow-up evaluations, or for any other reason as determined by the Investigator.
- **Subject Lost to Follow-Up** – If the Investigator has attempted to contact a subject at least three (3) times and receives no response, the subject may be lost to follow-up. The research staff should document at minimum three (3) attempts to contact the subject prior to terminating the subject from the trial, one of which should be a registered letter to the subject's address.
- **Subject Death** - When a subject expires, the Serious Adverse Event and Report of Patient Death must be completed in the data collection system. must be completed promptly. Source documents such as death summary, autopsy report (if done), and a copy of the death certificate should be redacted of personal identifiers and provided to the designated clinical monitor and DSMB to describe the cause of the subject's death. The Investigator will notify Sponsor or designated CRO within 24 hours of learning of the event.

The Study Exit Case Report Form should be completed for each study subject, to record date and reason for early termination (if subject does not complete the study) or at the final visit (if subject completes all study time points).

The Sponsor or the designated CRO will notify the competent authority of Serious Adverse Events in accordance with national regulations and requirements. .

4.34 Concomitant medications

To be eligible for enrollment, study participants be taking a minimum of three (3) anti-hypertensive medications at the time of entry into the study. Additionally, all subjects will remain on at least three (3) anti-hypertensive medications for the duration of the study, ideally the same medications at the same dosages.

Appropriate management of subject's individual risk factors such as statins, smoking cessation, nutrition, diabetes will remain as standard of care and any changes to this regimen will be documented by the study team.

Subjects should be advised of the importance of continuing their medical therapy regimen. Subjects should not reduce or stop their anti-hypertensive medication dosage until the 6-month time point, at which time the Principal Investigator may decide to reduce medication per the site's standard of care protocol.

All medications will be recorded on the Concomitant Medication log.

 neuroloop	Confidential	Protocol – The baroloop Study
--	---------------------	-------------------------------------

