4.18. Procedural Treatment and Timing

4.18.1. Medication Regimen

All participants in the study will be on a minimum of three (3) anti-hypertensive drugs such as, but not limited to, a diuretic (usually a thiazide or loop diuretic), a calcium channel blocker and an angiotensin converting enzyme inhibitor. Patients may be on additional antihypertensive drugs such as alpha- or beta-blockers, direct acting vasodilators angiotensin receptor blockers or combinations of these drugs. Where possible, simpler (fewer drug) regimens are preferred. Regardless of the of the particular three or greater combination of drugs, every effort should be made to maintain each patient on a stable regimen of antihypertensive medicines during the course of the study.

4.19. Baseline Assessment: Visit 1

The following information will be assessed, and the documentation will be maintained as source records at the study site:

- Medical history;
- Office cuff blood pressure;
- Check for orthostatic blood pressure and orthostatic pulse assessments;
- Current medication history including all hypertensive medication;
- Physical examination;
- Laboratory testing;
- Quality of Life SF-36 questionnaire.

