6.1. Overview

The primary objective of this study is to characterize the safety and feasibility of the baroloop System in subjects with uncontrolled or resistant hypertension. All subjects will be followed on an intent-to-treat basis (ITT). The device performance will also be assessed based on a per-protocol analysis of the primary safety and feasibility endpoints and secondary efficacy endpoints. An intent-to-treat analysis, along with other secondary analyses, will also be completed and reported.

This is not a hypothesis driven study, and no formal power analysis or hypothesis-driven statistical analysis has or will be performed. Standard summary statistics will be calculated for all study variables. For continuous variables, statistics will include means, standard deviations, medians and ranges. Categorical variables will be summarized using frequency distributions.

The primary endpoints will be analyzed on an intent-to-treat (ITT) basis, for which data from all subjects enrolled will be included. In order to evaluate a true treatment effect, the primary analysis will include those subjects achieving technical success, the definition of which includes successful completion of the study procedure.

If there are no more than 4 failures to implant, combined with a safety level that is determined by the independent DSMB to be acceptable, together with any reduction in blood pressure as a result of the baroloop therapy, this will be considered a successful outcome to this First-in-Human study.

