6.4. Secondary Endpoints

- The change in blood pressure recorded during intraoperative stimulation at the time of implantation.
- Mean reduction in 24-hour ambulatory systolic and diastolic blood pressure (ambulatory blood pressure monitoring - ABPM) at one (1), three (3), six (6), twelve (12) and eighteen (18) and twenty-four (24) months post-treatment versus baseline.
- The composite MAE rate at 1, 3, 6, 12, 18 and 24 months post-procedure defined:
 - All-causes of death
 - Hospitalization for hypertensive crisis post-titration
 - Any device or procedure-related serious adverse event
- The mean reduction in office diastolic and systolic blood pressure, and diastolic and systolic blood pressure at 1, 3, 6, 12, 18, and 24 months.
- Changes in antihypertensive medicines/doses through 1, 3, 6, 12, 18 and 24 months post-implantation as analyzed by Daily Defined Dosages (WHO Definition) and total medications.
- Quality of Life as measured by the Medical Outcomes Study 36-Item Short-Form Health Survey (SF-36).

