6.6. Imputation of Missing Data

Imputations for missing data in (e.g. withdrawn subjects, loss to follow-up, missing data) will not be performed. Analyses will be performed with all available data only.

7. Adverse Event and Incident Reporting

The occurrence of Adverse Events will be monitored during this study. All Adverse Events will be recorded on the Adverse Event Form and followed until resolved. The study will be conducted in accordance with EN ISO 14155: 2018-08: Clinical investigation of medical devices for human subjects - Good Clinical Practice. All Serious Adverse Event will be adjudicated by an independent DSMB and adjudicated results will be included in the data analysis.

 neuroloop	Confidential	Protocol – The baroloop Study
--	---------------------	-------------------------------------

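### Ambulatory and office BP reductions are summarised without regard to antihypertensive drug changes, and the success rule gives no way to attribute a fall in BP to the device

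*Combined protocol and SAP*

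**What the plan says.** **Drug rules.** Section 4.34 states "Subjects should not reduce or stop their anti-hypertensive medication dosage until the 6-month time point", and that from then "the Principal Investigator may decide to reduce medication per the site's standard of care protocol". It also says "all subjects will remain on at least three (3) anti-hypertensive medications for the duration of the study", and adds "ideally the same medications at the same dosages". Section 4.18.1 says "every effort should be made to maintain each patient on a stable regimen of antihypertensive medicines during the course of the study". No section prohibits adding a drug or raising a dose.

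**BP endpoints.** Section 6.4, repeating 4.3, lists the BP change during intraoperative stimulation, the mean reduction in 24-hour ABPM against baseline at 1, 3, 6, 12, 18 and 24 months, and "The mean reduction in office diastolic and systolic blood pressure, and diastolic and systolic blood pressure at 1, 3, 6, 12, 18, and 24 months". Drug changes, by WHO defined daily dose (DDD) and number of drugs, are a separate secondary endpoint at the same six times.

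**Analysis.** Section 6.6 covers missing data: no imputation, and "Analyses will be performed with all available data only". It does not address readings taken after a drug change. Section 6.1 mentions a per-protocol analysis but does not define it by drug stability. Its success rule combines at most four implant failures, safety acceptable to the DSMB, and "any reduction in blood pressure as a result of the baroloop therapy".

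**Comparator.** The synopsis (Statistical Model) has each subject as his or her own control and compares outcomes qualitatively with historical device results.

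**The concern.** Without a control arm, a lower ABPM or office BP at month 3 or 6 can come from stimulation, from a drug added since implantation, or from both. Up to month 6 the one explicit restriction is on the drug change that would raise BP; the change that would lower it is only discouraged. From month 6, reductions become possible at up to three sites, each following its own standard of care, and these work against the device in the later means.

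The occasion for intensifying drugs is real. Subjects have resistant hypertension, and section 4.24 foresees titration that may run beyond 12 sessions with intervals then extended up to six weeks, so a subject may stay above target for months.

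The BP endpoints are secondary and descriptive, but BP also enters the overall success statement in 6.1, and section 4.1 counts the ability to lower BP as part of feasibility. What is at stake is whether the reported BP change, and a declaration of success resting on it, can be read as an effect of the therapy.

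**Working it through.** The plan has no figure to reproduce: section 6.1 says there is no power analysis, and it gives no expected effect or standard deviation. What follows is illustration. The drug effects, the numbers of subjects changed and the standard deviations are assumptions.

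**Inputs from the documents**
- N: up to 10 subjects (4.4). If ten are enrolled and four implants fail, which 6.1 tolerates, N = 6.
- Background reference: about 3.6 mmHg, from the baroreflex activation therapy meta-analysis described in 2.5.1. It is context, not a threshold in the plan.

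**Assumptions**
- An added drug or dose increase lowers BP by x = 5 to 10 mmHg in the subject concerned; withdrawal or reduction raises it by the same amount.
- SD of the individual BP change: 10 to 20 mmHg.

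**1. Inflation by increases.** If m subjects are intensified and the device does nothing, the mean falls by m·x/N.

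| N | m | Shift, x = 5 to 10 mmHg |
|---|---|---|
| 10 | 2 | 2×5/10 to 2×10/10 = 1.0 to 2.0 |
| 10 | 5 | 5×5/10 to 5×10/10 = 2.5 to 5.0 |
| 6 | 2 | 2×5/6 to 2×10/6 = 1.7 to 3.3 |

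**2. What it takes to reach 3.6 mmHg.** Solve x = 3.6·N/m.
- N = 10, m = 3: 3.6×10/3 = 12 mmHg per subject, above the assumed range.
- N = 10, m = 5: 3.6×10/5 = 7.2 mmHg.
- N = 6, m = 3: 3.6×6/3 = 7.2 mmHg.

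**3. Chance of seeing any mean reduction with no device effect.** For a normal mean this is Φ(shift ÷ (SD/√N)), here with N = 10.
- Shift 0: 0.50, whatever the SD.
- Shift 2 mmHg: Φ(2 ÷ (20/√10)) = 0.62 to Φ(2 ÷ (10/√10)) = 0.74.
- Shift 4 mmHg: 0.74 (SD 20) to 0.90 (SD 10).

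So a sign-only reading of mean BP is met half the time by chance, and more often once drugs are added.

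**4. Masking by reductions from month 6.** Suppose a true device effect of 3.6 mmHg, with m of 10 subjects losing x mmHg of drug effect. The observed mean is 3.6 − m·x/10.
- m = 2: 3.6 − 1.0 = 2.6 to 3.6 − 2.0 = 1.6 mmHg.
- m = 5: 3.6 − 2.5 = 1.1 to 3.6 − 5.0 = −1.4 mmHg.

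**5. Which BP data are exposed.** ABPM and office BP at months 1 to 24 are. The intraoperative response is not, because it precedes any later drug change. Nor are the titration readings in 4.24 (continuous Finapres at baseline, during stimulation and in recovery, with cuff readings one minute into stimulation and one minute after it stops), because they compare on with off within one session.

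**The case against.** The strongest defence is that the plan does not ignore drugs. Changes are recorded at visits and on the medication log, and have their own endpoint at the same time points as BP. ABPM is done after observed intake, with compliance testing. With at most ten subjects and descriptive analysis, a reader could lay the two sets of results side by side. This stands in part: the gap is a missing link, not missing data. Observed intake, however, shows that the prescribed drugs were taken, not that the prescription was unchanged.

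Several stronger readings are tempting, and the documents do not support them:
- *Stable drugs are the only basis for attribution.* The on/off titration readings also give within-subject evidence, though acute only.
- *Additions are freely allowed and the rule flips at month 6.* The stability wording in 4.18.1 covers both directions and runs throughout the study. It is soft, but it does not lapse. After month 6 the bias is mixed, not simply reversed.
- *The three-drug minimum contradicts the permission to reduce.* A dose can be lowered, or a fourth drug dropped, with three still in place. The clearer tension is between 4.18.1 (stable regimen throughout) and 4.34 (reduction possible from month 6).
- *A drug-induced fall satisfies the success rule.* The rule requires the fall to result from the therapy. The fault is that it gives no means of showing this.
- *A few intensified subjects would readily reproduce 3.6 mmHg.* Three of ten would need 12 mmHg each, and nothing in the documents predicts how many subjects will be intensified.

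**Conclusion.** The point holds for 24-hour ABPM and office BP. Their mean reductions can mix drug and device effects, upward through increases and downward through reductions from month 6, and the plan has no analysis that separates the two. The success rule compounds this by leaving measure, time point and attribution open.

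On assumed effects of 5 to 10 mmHg per changed drug, two of ten subjects move the mean by 1 to 2 mmHg, or by 1.7 to 3.3 mmHg if only six are implanted. That is material beside the 3.6 mmHg background figure, but it rests on assumptions about how many regimens change and by how much.

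It does not follow that all BP evidence is compromised, or that any observed fall would be due to drugs. The intraoperative endpoint, the acute titration readings and the primary safety and technical feasibility endpoints are untouched. This is a cheap improvement worth making before data are reviewed, not a reason to doubt the design as a whole.

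**What to change.** In SAP 6.1 and 6.4:

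1. Keep the means from all readings.
2. Pre-specify beside them a summary of ABPM and office BP change limited to subject-visits where DDD and number of antihypertensives are unchanged or lower than at baseline. Print the number of subject-visits excluded.
3. At each time point, show BP change by regimen status (unchanged, increased, reduced), with a per-subject listing of BP next to DDD. Classify each reading, including month 6, by the regimen in force when it was taken.
4. State the measure and time point for the BP part of the success rule, and that it is read from the summary in item 2.

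Scoring intensified subjects as zero reduction is another possible estimand, but a debatable one: a substitution made for tolerability could raise DDD and erase a real effect.

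The sponsor should also reconcile 4.18.1 with 4.34 on regimen stability, the three-drug minimum and later reductions. Which clinical rule applies is for the sponsor; none is proposed here.

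The cost is SAP wording, one or two tables and a listing from data already on the medication log. The restricted summary will have fewer readings and may show a smaller reduction. Since intensified subjects may be the poorer responders, leaving them out could also favour the device, which is why the all-readings means and the exclusion counts must sit beside it.

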4.35 Study Exit or Premature Withdrawal

Subjects will be exited from the study by completion of a Study Exit form in the data collection system at the time of study completion provided the subject has not experienced an adverse event that is ongoing and unexplained.

Subjects may be terminated or withdrawn from the study early for, including but not limited to, the following reasons:

- Subject death.
- Voluntary withdrawal – meaning that the subject voluntarily chooses not to further participate in the study.
- Lost to follow-up – meaning that the subject is more than 14 days late to a study visit and 3 documented attempts to contact the subject are unsuccessful. A subject who misses a study visit but attends a subsequent visit will no longer be considered lost to follow-up. A missed visit will be considered a protocol deviation and the deviation will be documented and reported.
- In the physician's opinion, it is not in the best interest of the subject to continue study participation.

All subjects enrolled (including those withdrawn or lost to follow-up) shall be accounted for and documented.

5. Risk Benefit Assessment

Sponsor has conducted an analysis of the benefits and risks of the baroloop System and procedures necessary for implantation and use of the baroloop System. A detailed Risk Assessment has been completed, and the conclusion of this review is that this investigational study is justified because the overall potential benefit to the population outweighs its attendant risks.

5.1. Potential Adverse Events

There are Adverse Events associated with any endovascular / cardiovascular intervention and complications may develop. The following anticipated events have been identified as possible complications of transcatheter procedures in general and these and others may be associated with the baroloop System:

5.2. Potential risks

Adverse events which might occur with the usage of baroloop are listed as below in alphabetical order and are based on potential risks which are reported during the usage of other vagus nerve stimulators and/or baroreflex activation therapy:

5.3. Potential Adverse Events

Surgery-related

- hematoma
- infection
- pain
- voice alteration (hoarseness)

Stimulation-related

- bradycardia
- dyspepsia (indigestion)
- dysphagia (difficulty swallowing)
- dyspnea (difficulty breathing, shortness of breath)
- hypotension
- increased coughing
- laryngismus (throat, larynx spasms)
- pain
- paresthesias (prickling of the skin)
- pharyngitis (inflammation of the pharynx, throat)
- satiety (reduced appetite)
- sensation of stimulation
- syncope
- voice alteration (hoarseness)

It is anticipated that subjects will be exposed to operative and post-operative risks similar to related surgical procedures involving the neck and/or a pacemaker implant. These risks and potential risks of chronic device based baroreflex activation may include, but are not limited to:

- Surgical or anesthetic complications
- Infection – the need for antibiotics or possible removal of the system
- Wound Complication –including hematoma (i.e. bruising and/or swelling)
- Arterial damage –including carotid artery rupture or hemorrhage (sudden and significant blood loss at a site of blood vessel rupture that may require reoperation or transfusion)
- Pain – an unpleasant sensory experience
- Nerve Damage/Stimulation –including injury to or stimulation of Cranial, Marginal Mandibular, Glossopharyngeal, Recurrent Laryngeal, Vagus and Hypoglossal Nerves (numbness in head and neck, facial palsy/paralysis, altered speech, altered sense of taste, respiratory constriction, stertorous breathing, excessive salivation, dry cough, vomiting and/or regurgitation, altered sensory and motor function of tongue, altered sensory function of pharynx and oropharynx, altered sensation in external auditory canal), stimulation of extravascular tissue (muscle twitching (fasciculation), pain, tingling, oral sensations)
- Hypotension – a decrease in systolic and diastolic blood pressure below normal levels that may result in dizziness, fainting, and/or falls
- Hypertensive crisis – uncontrolled rise in blood pressure
- Respiratory – including low oxygen saturation, respiratory distress, shortness of breath
- Exacerbation of heart failure

 neuroloop	Confidential	Protocol – The baroloop Study
--	---------------------	-------------------------------------

- Cardiac arrhythmias
- Tissue erosion/IPG migration – movement of device resulting in need for reoperation
- Fibrosis – replacement of normal tissue by the ingrowth of fibroblasts and the deposition of connective tissue
- Allergic Reaction
- General injury to user or patient –may be due to surgical procedure, device use, or interaction with other devices
- Need for reoperation – operation to explant/replace IPG or Cuff electrode or Lead due to tissue damage, infection, and/or device failure
- Secondary operative procedure –An increase in the complexity and risk of secondary operative procedures of the neck due to scar tissue and the presence of prosthetic material implanted for this device.
- Death

5.4. Potential Risks to Subject Confidentiality and Privacy

In all clinical studies, confidentiality of protected health information may be breached due to study-related activities beyond those of routine clinical care. This also includes risks of privacy and release of protected health information (PHI). This risk will be minimized through the use of a unique and anonymous study identification code. No identifying information will be reported in the data collection system or other study related documentation that is provided to the Sponsor.

5.5. Minimization of Anticipated Risks

Efforts to minimize risk include the following:

1. Clearly defining the subject inclusion / exclusion criteria.
2. Selecting a sufficient number of intended users and only qualified, experienced Investigators who have participated in a training program to assure thorough knowledge of the Investigational Plan and proper technique for implantation of the baroloop System.
3. Monitoring electrocardiographic and hemodynamic parameters during placement of the device to evaluate for any compromise of the subject's condition.
4. Ensuring that treatment and follow-up of subjects is consistent with standard and current medical practice.
5. Providing clinical support for device-related guidance during the implantation, titration and follow-up procedures.
6. Safety oversight by Medical Monitor and the DSMB for individual subjects as well as across the entire study population.
7. If the Investigator and / or the Medical Monitor or DSMB determine that an AE is sufficiently severe to remove the subject from the study, a termination assessment will be performed. The subject will then be given appropriate treatment under medical supervision.
8. If the Medical Monitor or DSMB determines a negatively high rate for a particular safety issue across the subject population, a termination assessment will be performed, and the Medical Monitor or DSMB may recommend enrollment in the study to be stopped.

PHI protection measures, such as use of a unique study identification code and a commitment from all participants to protect subject confidentiality at every step during the investigation, must be maintained.

